9.2 Study Procedures by Visit

Patients and their caregivers will be invited to participate in the study and will be issued with the patient information and informed consent or the personal legal representative information and informed consent (refer to [Section 9.1.2](#) and [Section 15.2](#)). Following adequate time to discuss the study with the investigator, nurse, relatives or caregiver, patients/legal representatives who provide written informed consent at Visit 1 will be screened for entry into the study.

9.2.1 Double Blind Phase

9.2.1.1 Visit 1 (Day -14 to -7, Screening)

The following observations will be made at Visit 1: demographics, medical history (including seizure information since diagnosis, history of epilepsy-specific genetic testing and all prior AEDs taken), concomitant medications (including AEDs), physical examination (including height and body weight), ECG, vital signs and AEs.

Clinical laboratory samples (blood and urine) will be taken for hematology, biochemistry, alcohol testing, THC testing, urinalysis and a pregnancy test (using a serum sample, if appropriate). The laboratory results should be available within 3-5 working days after Visit 1. If the results show a patient is ineligible, the patient will not be enrolled into the study. The C-SSRS will be administered.

Patients who satisfy all inclusion and none of the exclusion criteria specified in [Section 6](#) will be assigned a unique patient number and then begin the baseline period. Patients or their caregivers will be given a paper diary to record daily seizure information, rescue medication, concomitant AEDs and AEs; and will be instructed on how to do so. The investigator must record the patient's attendance at the visit and confirm the outcome of screening on the CRF.

9.2.1.2 Visit 2

9.2.1.2.1 Visit 2 (Day 1) – Enrollment (+ 3 days)

This visit will occur 7–14 days after Visit 1.

The following observations will be made at Visit 2: concomitant medications, (including AEDs), physical examination (including body weight), ECG, vital signs and review of patient diary and AEs.

Clinical laboratory samples (blood and urine) will be taken for hematology, biochemistry, alcohol testing and urinalysis. Blood samples will also be taken for genetic testing if additional consent has been obtained. The C-SSRS will be administered. The investigator must record the patient's attendance at the visit, and confirm the outcome of the visit prior to enrollment.

Following enrollment patients will begin the PK sampling process. Blood samples will be taken for analysis of plasma concentrations of CLB, N-CLB, VPA, STP, LEV and TPM. A baseline PK sample will be taken before the patient takes their morning dose of CLB. Further samples will then be taken at the following times relative to the CLB dose: 15 minutes, 30 minutes, 1 hour, 1.5 hours, 2 hours, 4 hours, 6 hours and 12 hours. The evening dose of any AEDs must be taken after the 12 hour PK blood sample. Patients will either remain in clinic overnight throughout this PK sampling process or return to the clinic on Day 2 ahead of additional sample collection.

9.2.1.2.2 Visit 2 (Day 2) - Enrollment

This is the second part of the two day enrollment visit. The final PK sample will be collected 24 hours after the Day 1 morning CLB dose.

Following completion of the PK sampling process the following observations will be made on Day 2: concomitant medications (including AEDs), physical examination (including body weight), vital signs and AEs.

GWP42003-P/placebo will be dispensed and both the morning dose of CLB and of GWP42003-P/placebo will be taken in clinic. Following administration of GWP42003-P/placebo, patients must remain in clinic for at least 30 minutes to monitor for any adverse reactions. Patients and/or their caregivers will be provided with individual dosing schedules as described in [Section 8.1.2](#). Each patient will then receive their GWP42003-P/placebo for the 10 day titration period followed by the 21 day maintenance period. Patients, or their caregivers, will be instructed on how to record the diary information.

9.2.1.3 Visit 3 (Day 12 +3 days)

This visit will occur 11 days after Visit 2, Day 1 (enrollment). Patients will return all used and unused GWP42003-P/placebo. The following observations will be made at Visit 3 (Day 12): concomitant medications (including AEDs), physical examination (including body weight), ECG, vital signs, AEs and review of patient diary completion.

Clinical laboratory samples (blood and urine) will be taken for hematology, biochemistry and urinalysis. The C-SSRS will be administered.

9.2.1.4 Visit 4

9.2.1.4.1 Visit 4 (Day 33) (\pm 3 days)

This visit will occur 32 days after Visit 2, Day 1 (enrollment). Patients will return all used and unused GWP42003-P/placebo. The following observations will be made at

Visit 4 (Day 33): concomitant medications (including AEDs), physical examination (including body weight), ECG, vital signs, review of patient diary and AEs.

Clinical laboratory samples (blood and urine) will be taken for hematology, biochemistry, alcohol testing, and urinalysis. The C-SSRS will be administered.

Blood samples will be taken for analysis of plasma concentrations of CLB, N-CLB, VPA, STP, LEV, TPM, CBD, CBD major metabolites, THC and THC major metabolites. A baseline PK sample will be taken before the patient takes their morning dose of CLB, followed immediately by their dose of GWP42003-P/placebo. Further samples will then be taken at the following times relative to the CLB dose: 15 minutes, 30 minutes, 1 hour, 1.5 hours, 2 hours, 4 hours, 6 hours and 12 hours. The evening dose of GWP42003-P/placebo and any AEDs must be taken after the 12 hour PK blood sample. Patients are expected to remain in clinic throughout this PK sampling.

The investigator must assess adherence to the dosing regimen and recording of rescue medications by reviewing the patient's diary.

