	
as advised by the investigator.
 
• If the patient does not enter the OLE period of the study, the patient will taper off of GWP42003-P by reducing the dose by approximately 10% of the maintenance dose each day until dosing has ceased, with end of taper on Day 43 (Visit 5). 
PK samples will be taken on the day of enrollment (Visit 2, Day 1) and after completing 21 days treatment on GWP42003-P or placebo (Visit 4, Day 33). The PK assessments will therefore capture the following combinations of CLB and GWP42003-P:
 
• First PK Assessment: CLB only.• Second PK Assessment: CLB and GWP42003-P or placebo. 
Each PK assessment should be performed at time points in respect to a morning dose of CLB. The time points are as follows: Pre-dose, 15 min, 30 min, 1 h, 1.5 h, 2 h, 4 h, 6 h, 12 h and 24 h. It is expected that the patient will continue to take their CLB as advised by their physician and PK assessments will be scheduled in order to accommodate this dosing schedule. The GWP42003-P/placebo should be taken twice daily immediately following their CLB dose.
 
PK assessments will analyze the amount of CLB, the CLB primary metabolite N-CLB, CBD, CBD major metabolites, Δ^9-tetrahydrocannabinol (THC), THC major metabolites, valproate (VPA), stiripentol (STP), levetiracetam (LEV) and topiramate (TPM). Patients will be required to keep a paper diary to note the time and dose of GWP42003-P and CLB administration each morning and evening and to record any adverse events (AEs) that may occur whilst receiving investigational medicinal product (IMP) and any other medications. Patients will also be requested to record the number and type of seizures for each day whilst on the study.

Primary Endpoint	
The primary endpoints of the study are the PK parameters (C_{max}, t_{max}, $AUC_{(0-\infty)}$ $AUC_{(0-t)}$, $t_{1/2}$) of the following analytes:
 
• CLB• N-CLB• CBD• CBD major metabolites
Secondary Endpoint(s)	
To assess the safety and tolerability of GWP42003-P compared with placebo when taken in combination with CLB. Safety and tolerability will be assessed using the following parameters:
 
• AEs• 12-lead electrocardiogram (ECG)• Clinical laboratory parameters (clinical chemistry, hematology and urinalysis)• Vital signs• Columbia-Suicide Severity Rating Scale (C-SSRS)• Seizure frequency

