
on Day 2 ahead of additional sample collection.

VISIT 2 - Enrollment (Day 2)

This is the second part of the two day enrollment visit. The final PK sample will be collected 24 hours after the Day 1 morning CLB dose. Following completion of the PK sampling process the following observations will be made on Day 2: concomitant medications (including AEDs), physical examination (including body weight), vital signs and AEs.

GWP42003-P/placebo will be dispensed and both the morning dose of CLB and GWP42003-P/placebo will be taken in clinic. Following administration of GWP42003-P/placebo, patients must remain in clinic for at least 30 minutes to monitor for any adverse reactions. Patients and/or their caregivers will be provided with individual dosing schedules as described in Section 8.1. Each patient will then receive their GWP42003-P/placebo for the 10 day titration period followed by the 21 day maintenance period. Patients, or their caregivers, will be instructed on how to record the diary information.

VISIT 3 – Day 12 + 3 day window

This visit will occur 11 days after Visit 2, Day 1 (enrollment). Patients will return all used and unused GWP42003-P/placebo. The following observations will be made at Visit 3: concomitant medications (including AEDs), physical examination (including body weight), ECG, vital signs, AEs and review of patient diary completion.

Clinical laboratory samples (blood and urine) will be taken for hematology, biochemistry and urinalysis. The C-SSRS will be administered.

VISIT 4 - Day 33 ± 3 days window

This visit will occur 32 days after Visit 2, Day 1 (enrollment). Patients will return all used and unused GWP42003-P/placebo. The following observations will be made at Visit 4 (Day 33): concomitant medications (including AEDs), physical examination (including body weight), ECG, vital signs, review of patient diary and AEs.

Clinical laboratory samples (blood and urine) will be taken for hematology, biochemistry, alcohol testing and urinalysis. The C-SSRS will be administered.

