4. EXPERIMENTAL PLAN

4.1 Study Design

This phase 2, placebo-controlled study consists of a 34 day, double-blind phase followed by an optional maximum one year OLE. Patients will continue to take CLB as advised by their physician for the duration of the study. GWP42003-P/placebo will be taken twice daily immediately after their CLB dose.

Patients will enter the study and begin a 10 day GWP42003-P or placebo titration phase. During this period patients will be up-titrated to a maintenance dose or equivalent of 20 mg/kg/day. Patients will continue to take this maintenance dose of GWP42003-P or placebo for 21 days (Days 12 to 32).

Upon completion of the treatment period (Day 34) patients will be invited to receive GWP42003-P during the OLE phase. If a patient enters the OLE they will take GWP42003-P as advised by the investigator. If a patient chooses not to enter the OLE, and/or the investigator does not feel it is in their best interests, they will taper off their GWP42003-P/placebo treatment by reducing their maintenance dose by 10% per day until dosing has ceased. For those patients not entering the OLE, dosing will end on Day 43 and they will receive a telephone follow-up visit four weeks after the end of GWP42003-P/placebo dosing (Day 71).

PK samples will be taken on two occasions during the blinded phase of the study:

- Day 1 (Visit 2) before beginning treatment (patients will be taking CLB only).
- Day 33 (Visit 4) following 21 days of GWP42003-P or placebo maintenance (patients will be taking CLB and GWP42003-P or placebo).

Ten samples will be taken during each PK assessment. PK samples should be taken at time points in respect to the morning dose of CLB. The time points are as follows: Pre-dose, 15 min, 30 min, 1 h, 1.5 h, 2 h, 4 h, 6 h, 12 h and 24 h. PK samples will be quantitatively analyzed for CLB, N-CLB, valproate (VPA), stiripentol (STP), levetiracetam (LEV) and topiramate (TPM) at Visit 2 and CLB, N-CLB, VPA, STP, LEV, TPM, CBD, CBD major metabolites, THC and THC major metabolites at Visit 4.

Patients should try to be consistent in the timing of their food intake in relation to dosing throughout the blinded phase of the study.

Upon entry into the OLE the dose of GWP42003-P and other AEDs may be adjusted up or down to a maximum of 30 mg/kg/day. The OLE will last for a maximum of one year or until marketing authorization is granted; whichever is earlier.

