8.1.2 Dose Escalation and Dose Adjustments

Patients will enter the blinded phase of the study and will be up-titrated over ten days (Day 2 to Day 11) to a maintenance dose or equivalent of GWP42003-P/placebo of 20 mg/kg/day. If GWP42003-P is not tolerated then the dose can be reduced accordingly at the discretion of the investigator. The titration regimen is described in [Table 8.1.2-1](#).

Table 8.1.2-1 Dose Up-titration Regimen*			
Day - GWP42003-P/Placebo (Blinded Period)	Dose Level (GWP42003-P or equivalent placebo)	Open label Extension** (GWP42003-P only) Day	Dose Level GWP42003-P
2	2.5 mg/kg	34	2.0 mg/kg
3	2.5 mg/kg	35	4.0 mg/kg
4	5.0 mg/kg	36	6.0 mg/kg
5	5.0 mg/kg	37	8.0 mg/kg
6	7.5 mg/kg	38	10.0 mg/kg
7	7.5 mg/kg	39	12.0 mg/kg
8	10.0 mg/kg	40	14.0 mg/kg
9	10.0 mg/kg	41	16.0 mg/kg
10	15.0 mg/kg	42	18.0 mg/kg
11	15.0 mg/kg	43	20.0 mg/kg
12 onwards	20.0 mg/kg	44	20.0 mg/kg***

* GWP42003-P /placebo is to be taken twice daily. Total daily doses are shown.

** Only patients who were taking placebo during the double-blind period will up-titrate according to this schedule during the OLE period. Those taking GWP42003-P during the double-blind period will down-titrate their blinded IMP whilst simultaneously up-titrating with GWP42003-P, thus maintaining a daily dose of 20 mg/kg/day GWP42003-P throughout.

*** The GWP42003-P dose of 20 mg/kg/day can be adjusted during the OLE period, after Visit 5, at the investigator's discretion: up to a maximum dose of 30 mg/kg/day. It may also be adjusted down (no minimum).

The titration regimen defined above should be followed to the maximum dose (20 mg/kg/day). Should an AE occur during titration which is attributable to IMP or concomitant AED, then IMP dose should be reduced to the next lower dose. Any other changes in concomitant AED therapy should be reviewed with the medical monitor before being initiated.

For those patients who do not enter the OLE the dose of GWP42003-P/placebo will taper off over 10 days beginning on Day 34. The patient will reduce the dose by 10% of the maintenance dose each day and treatment will end on Day 43.

Patients who enter the OLE period will be transitioned to the OLE treatment over a 10-day period in order to maintain blinding, simultaneously down-titrating blinded GWP42003-P /placebo whilst up-titrating open-label GWP42003-P. As such, patients

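### The Visit 4 window lets the only on-treatment PK profile be taken after 18 maintenance days instead of the stated 21, and the N-CLB troughs planned cannot show whether a plateau was reached

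*Protocol*

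**What the plan says.** Section 8.1.2 states that patients "will be up-titrated over ten days (Day 2 to Day 11", and Section 4.1 that they then take the "maintenance dose of GWP42003-P or placebo for 21 days (Days 12 to 32". Section 4.1 defines the on-treatment profile as "Day 33 (Visit 4) following 21 days of GWP42003-P or placebo maintenance", and the synopsis (Study Design) places it "after completing 21 days treatment on GWP42003-P or placebo (Visit 4, Day 33".

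The operative visit text is looser. Section 9.2.1.4.1 gives the nominal day, "This visit will occur 32 days after Visit 2, Day 1 (enrollment", under a heading that allows 3 days either way. The synopsis (Procedures) has "VISIT 4 - Day 33 ± 3 days window", and Appendix 1 agrees. Visits 2 and 3, by contrast, can be up to 3 days late but not early.

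Section 4.1 says "PK samples will be taken on two occasions during the blinded phase of the study": Day 1, before any CBD, and Day 33. At Visit 4, "A baseline PK sample will be taken before the patient takes their morning dose of CLB", and Section 9.2.1.4.2 adds a last sample 24 hours after that dose. Visit 3 has safety bloods but no PK sample. The protocol gives no half-life for N-CLB and no reason why 21 days is enough.

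**The concern.** A site can follow the visit section to the letter and still miss the condition that defines the profile. Visit 4 carries the primary endpoint, yet unlike the two visits before it, it may be early.

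N-CLB is the analyte exposed. It is one of the two analytes in the primary objective. If CBD slows its elimination, its new level takes longer to reach, so the largest interactions would be furthest from plateau when sampled. The N-CLB ratio would then understate the change, and a pre-treatment profile plus a single on-treatment profile give little means of noticing it.

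**Working it through.** **Day count.** Days 12 to 32 make 32 − 12 + 1 = 21 days, which reproduces the protocol's figure. Maintenance days completed before a visit on day V are V − 12:

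- Day 30: 18
- Day 33: 21
- Day 36: 24

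**Approach to the new N-CLB level.** The inputs from the protocol are the Table 8.1.2-1 doses: 2.5, 2.5, 5, 5, 7.5, 7.5, 10, 10, 15 and 15 mg/kg on Days 2 to 11, then 20. These titration doses sum to 80 mg/kg, equal to 80/20 = 4 full-dose days. Three things are assumed: N-CLB half-life T on CBD is 2 to 10 days, T is constant, and the effect is proportional to dose.

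With x the share of the final change reached and x = 0 at the start of Day 2, each day gives x(next) = D/20 + (x − D/20)·2^(−1/T). From Day 12 this reduces to x = 1 − (1 − x12)·2^(−d/T), where d is the number of maintenance days.

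| T (days) | x12 | Day 30 (d = 18) | Day 33 (d = 21) | Cost of Day 30 |
|---|---|---|---|---|
| 2 | 0.566 | over 99% | over 99% | under 0.1 point |
| 7 | 0.289 | 1 − 0.711 × 0.168 = 88.0% | 1 − 0.711 × 0.125 = 91.1% | 3.1 points |
| 10 | 0.221 | 1 − 0.779 × 0.287 = 77.6% | 1 − 0.779 × 0.233 = 81.8% | 4.2 points |

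At T = 10 the shortfall is already 18 points on Day 33; the early visit adds about 4. Leaving titration out gives 83% / 88% at 7 days and 71% / 77% at 10 days, which overstates the shortfall.

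**The two Visit 4 troughs.** At T = 10 the share gained in the 24 hours after Day 33 is 0.182 × (1 − 2^(−0.1)) = 0.182 × 0.067 = 0.012. For a final ratio of 2, the trough moves by 0.012/1.818, or about 0.7%. In a variant where an assumed baseline half-life of 1 to 3.5 days lengthens in proportion to a final ratio of up to 5, the one-day change from Day 30 is still at most about 1.7%, even with 38% of the rise missing. The 24-hour sample has a window of 1 hour either way (Section 9.1.10). Such a pair cannot show a plateau.

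**The no-effect rule.** Section 13.6.3 requires the 90% CI to lie within 0.5 to 2.0. Assume 20 × 4/5 = 16 active patients, a paired comparison and a within-subject CV of 20 to 40%. Then s = √ln(1 + CV²), SE = s·√(2/16), and the estimate must fall below 2·exp(−1.753·SE), where 1.753 is the 95th percentile of t on 15 df.

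- CV 20%: s = 0.198, SE = 0.070, cut-off 1.77.
- CV 40%: s = 0.385, SE = 0.136, cut-off 1.58.

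On Day 30 a true ratio of 2.0 reads on average 1 + 0.880 = 1.88 at T = 7 and 1 + 0.776 = 1.78 at T = 10. A true ratio of 2.2 at T = 10 reads 1 + 1.2 × 0.776 = 1.93. Only the first case at T = 10 with CV 20% comes near its cut-off (1.78 against 1.77); on Day 33 it reads 1.82.

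**The case against.** The other side is strong on size. Day 33 with 3 days either way is an ordinary visit window, and it is symmetric: late visits reach 24 maintenance days and partly offset early ones. The window is the smaller cause, since most of any shortfall exists at the nominal 21 days. The harm also needs a half-life that the protocol does not give, and at 2 days there is none. The direction is open too: Sections 3.3 and 3.4 allow for inhibition or induction, and faster elimination would bring the plateau sooner. All of this stands, and it limits the point to one of consistency with a modest, conditional effect on the estimate.

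A reader might infer that the timing favours a no-effect result in general. The rule does not support that. The whole interval must lie inside the limits, and in the ranges above the expected reading for true ratios of 2.0 or more stays above the cut-off, narrowly so only at the limit itself.

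A reader might also infer that no sample bears on the plateau at all. That is too absolute, because Visit 4 has a pre-dose and a 24-hour trough. They are simply too close together.

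What the objection does not remove is the conflict in the text. It needs no assumption, and sampling days that were never scheduled cannot be recovered in the analysis.

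**Conclusion.** The protocol contradicts itself: the profile is defined as following 21 maintenance days, yet it may be taken after 18. It also has no usable check that N-CLB has levelled off. Under an assumed half-life of 2 to 10 days on CBD, constant and with an effect proportional to dose, an early visit costs at most about 4 percentage points of the final change. The total shortfall on Day 33 runs from under 1 point to about 18.

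The consequence is a possibly understated size of the N-CLB change. A false declaration of no meaningful effect is a concern only for true ratios close to 2.0 combined with slow elimination. The protocol does not support concluding that 21 days is too short or that the N-CLB ratio will be biased. It only leaves both unaddressed.

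**What to change.** Make the Visit 4 PK window plus-only (Day 33, +3 days) in the synopsis, Section 9.2.1.4.1 and Appendix 1, matching Visits 2 and 3. Every profile then follows at least the stated 21 maintenance days. No exposure is added beyond the Day 36 already allowed. The cost is less scheduling freedom at Visit 4.

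Optionally, add one timed pre-dose CLB/N-CLB sample to the blood draw already scheduled at OLE Visit 5, two weeks after Day 34. Use it only in patients randomized to GWP42003-P whose CLB, GWP42003-P and other AED doses are unchanged. If N-CLB is clearly higher than at Visit 4, report the Visit 4 N-CLB ratio as a possible underestimate. Define in advance what counts as clearly higher, because the expected difference is small. By Day 48 (d = 36) the shares are 98.0% at T = 7 and 93.6% at T = 10, so for a final ratio of 2 the trough rises by 1.980/1.911 − 1 = 3.6% and 1.936/1.818 − 1 = 6.5%. The cost is a timed morning dose at that visit, and the sample exists only for patients who enter the extension.

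A Visit 3 sample would not serve this purpose. Day 12 is the first full-dose day, so a rise from Visit 3 to Visit 4 is expected whether or not a plateau follows.

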9.1.10 Pharmacokinetic Analyses

The plasma concentration/time curves of CLB, N-CLB, VPA, STP, LEV and TPM will be assessed at Visit 2 (Day 1 and Day 2) and CLB, N-CLB, VPA, STP, LEV, TPM, CBD, CBD major metabolites, THC and THC major metabolites at Visit 4 (Day 33 and Day 34). Patients will be given their daily dose of CLB at a scheduled time during Visit 2 and Visit 4 and the GWP42003-P/placebo immediately afterwards (Visit 4 only) to facilitate the accurate timing of blood samples required for PK analysis. Blood samples will be taken by either direct venipuncture or an indwelling cannula inserted into a forearm vein at the following times: Pre-dose and, 15 minutes, 30 minutes, 1 hour, 1.5 hours, 2 hours, 4 hours, 6 hours, 12 hours and 24 hours after dosing. The timing of each PK sample will be relative to the morning dose of CLB.

The pre-dose blood sample will be taken within 30 minutes prior to dosing. The allowable window for post-dose blood sample collection is \pm 2 minutes up to and including 1 hour post-dose, \pm 5 minutes from 1.5 hours up to and including 6 hours post-dose and \pm 1 hour at 12 hours and 24 hours post-dose.

In the event of an AE that, in the opinion of the investigator, is related to a concomitant AED, additional blood samples may be collected.

Analysis of all PK samples will be conducted at a central clinical laboratory. Sample volume requirements and processing procedures will be detailed in a separate laboratory manual.

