9.2.1.4.2 Visit 4 (Day 34)

This is the second part of the two day visit. The final PK sample will be collected 24 hours after the Day 33 morning CLB dose.

Following completion of the PK sampling process the following observations will be made on Day 34: concomitant medications (including AEDs), physical examination (including body weight), vital signs and AEs.

At the end of the blinded phase of the study on Day 34, providing the investigator and patient both agree, patients will be invited to continue taking GWP42003-P and to enter the OLE.

Patients who enter the OLE will be dispensed GWP42003-P on Day 34 and the first dose will be taken in clinic. Following administration of GWP42003-P, patients must remain in clinic for at least 30 minutes to monitor for any adverse reactions. At the point of entry to the OLE, patients will be transitioned to the OLE treatment over a 10 day period in order to maintain blinding.

Patients who do not enter the OLE will begin a 10 day taper period during which they will taper off their daily dose of GWP42003-P/placebo. The daily dose will be reduced by 10% of the maintenance dose per day and treatment will end on Day 42.

9.2.1.5 Visit 5 (Patients not entering Open Label Extension) (Day 43 + 3 days)

This visit will occur 42 days after Visit 2, Day 1 (enrollment) for those patients who do not enter the OLE.

All GWP42003-P/placebo (used and unused) will be collected and a check of the returned GWP42003-P/placebo against usage must be made. A physical examination (including body weight), ECG and vital signs will be assessed and the C-SSRS will be administered. The trained investigator or study coordinator will complete the Study Medication Use and Behavior Survey as an interview with the patient/caregiver. Clinical laboratory samples (blood and urine) will be taken for hematology, biochemistry and urinalysis and a review of concomitant medications (including AEDs) and AEs will be completed. Patient diaries will be collected.

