13.6 Endpoints and Statistical Methods

13.6.1 Primary Endpoint(s)

The primary endpoints of the study are the PK parameters (C_{max} , t_{max} , $AUC_{(0-\infty)}$, $AUC_{(0-t)}$, $t_{1/2}$) of the following analytes:

- CLB
- N-CLB
- CBD
- CBD major metabolites

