13.6.3 Pharmacokinetics

Calculation of PK parameters will be based on actual blood sampling times [h] (relative to the corresponding administration time) rounded to two decimal digits with negative pre-dose times set to zero. Plasma concentrations of CLB, N-CLB, VPA, STP, LEV, TPM, CBD, CBD major metabolites, THC and THC major metabolites will be displayed graphically, summarized and listed. For descriptive statistics, values below the lower limit of quantification of the assay (LLOQ) will be excluded from any calculations. Descriptive statistics of concentrations will be calculated if at least half of the individual data points that have been measured are equal to or above the LLOQ.

For calculation of the PK parameters, the following rules will be applied:

At time zero and at time points in the lag-time between time zero and the first quantifiable concentration, concentrations below the LLOQ will be set to zero. All other concentrations below the LLOQ will not be used in calculations.

Variables derived from plasma concentrations:

- Concentration maximum (C_{\max}): Highest observed plasma concentration of the measured concentration-time profile. Dimension: [amount / volume].
- Terminal half-life $t_{1/2} = \ln(2)/\lambda_z$.
- The rate constant of the terminal phase λ_z will be determined by linear regression of log-transformed concentration data after the time of maximum concentration. A sequence of terminal elimination rate constants will be created by linear regression. Linear regressions are repeated using the last three points with a quantifiable concentration, the last four points, the last five points etc. For each regression, an adjusted R^2 is computed. The regression with the largest adjusted R^2 is selected to estimate the terminal half-life. Dimension: [time].
- Area under the concentration-time curve from administration until the last sampling point (t) equal or above the LLOQ $AUC_{(0-t)}$ will be calculated by the linear trapezoidal formula. Dimension: [time • amount / volume].
- Area under the concentration-time curve extrapolated to infinity: $AUC_{(0-\infty)} = AUC_{(0-t)} + C_{\text{last}}/\lambda_z$ and C_{last} is the concentration observed at the last time point with a quantifiable concentration, λ_z refers to the terminal elimination rate constant. Dimension: [time • amount / volume].
- Time of maximum concentrations: T_{\max} will be taken as the time after administration at which C_{\max} occurs. Dimension: [time].

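### On Day 33 the evening dose falls between the 12 h and 24 h samples, so the rules in 13.6.3 do not give a valid half-life, AUC(0-t) or AUC(0-∞) for CBD, its metabolites or THC

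*Protocol*

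**What the plan says.** - **Dosing.** Protocol 4.1: "GWP42003-P/placebo will be taken twice daily immediately after their CLB dose".
- **PK day.** Protocol 9.2.1.4.1 (Day 33): "The evening dose of GWP42003-P/placebo and any AEDs must be taken after the 12 hour PK blood sample". Protocol 9.2.1.2.1 has the matching rule for Day 1: "The evening dose of any AEDs must be taken after the 12 hour PK blood sample".
- **Sampling.** After the pre-dose sample, Protocol 9.1.10 lists "15 minutes, 30 minutes, 1 hour, 1.5 hours, 2 hours, 4 hours, 6 hours, 12 hours and 24 hours after dosing", all timed from the morning CLB dose. Protocol 9.2.1.4.2 confirms: "The final PK sample will be collected 24 hours after the Day 33 morning CLB dose". Nothing is drawn between 12 h and 24 h.
- **Calculation.** Protocol 13.6.3, on the terminal slope: "Linear regressions are repeated using the last three points with a quantifiable concentration, the last four points, the last five points etc". The fit with the largest adjusted R² is kept. AUC(0-t) is a linear trapezoid to the last quantifiable sample, and AUC(0-∞) adds the last concentration divided by the terminal slope. No rule covers a sample drawn after a further dose.
- **Status.** Protocol 13.6.1: "The primary endpoints of the study are the PK parameters", namely Cmax, tmax, AUC(0-∞), AUC(0-t) and t1/2, for CLB, N-CLB, CBD and CBD major metabolites. THC and its metabolites are secondary (13.6.2).
- **CLB frequency.** Protocol 9.1.10 implies one dose a day: "Patients will be given their daily dose of CLB at a scheduled time during Visit 2 and Visit 4". The diary instruction in 4.1 expects CLB entries both morning and evening.

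**The concern.** The formulas in 13.6.3 suit a profile in which concentration keeps falling after one dose. Here a second dose enters after the 12 h sample. After 21 days of maintenance, the 12 h and 24 h samples are both end-of-interval troughs of about equal height.

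Three primary-endpoint parameters of CBD and its metabolites are then affected in active patients (16 of 20 at 4:1) whose 24 h value is quantifiable:
- The slope is fitted across two troughs.
- The last trapezoid passes under an evening peak that is never sampled.
- AUC(0-∞) combines both errors.

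The same mechanism reaches CLB and N-CLB in any patient who also takes CLB in the evening.

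**Working it through.** The protocol states no half-life or AUC, so there is no figure to reproduce. The check applies its own rules to noise-free profiles.

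**Inputs from the protocol.** Samples at 0, 0.25, 0.5, 1, 1.5, 2, 4, 6, 12 and 24 h; dosing every 12 h; evening dose just after the 12 h sample; slope and AUC rules of 13.6.3.

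**Assumptions (not in the documents).** One compartment, half-life 3-36 h, absorption rate ka 0.8-2 per h, steady state.

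**Formulas.** Single dose: C(t) = ka/(ka−ke) × (e^(−ke·t) − e^(−ka·t)), with ke = ln 2 / t1/2. Steady state: the sum of C(t + 12k) over k = 0, 1, 2, …, so 12-24 h repeats 0-12 h.

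**One case in full: t1/2 = 6 h, ka = 1.5.** Concentrations at 2, 4, 6, 12 and 24 h are 1.093, 0.907, 0.722, 0.361 and 0.361.
- Slope: the last 3 points give t1/2 21.0 h (adjusted R² 0.14), the last 4 give 15.7 h (0.55) and the last 5 give 13.6 h (0.68). The rule selects 13.6 h; the truth is 6 h.
- AUC: trapezoid 0-12 h = 8.755. The 12-24 h segment = (0.361 + 0.361)/2 × 12 = 4.33. Total 13.09. The true interval AUC is 1/ke = 8.656, so true 24 h exposure is 17.31. The ratios are 13.09/17.31 = 0.76 and 13.09/8.656 = 1.51, so AUC(0-t) matches neither exposure.

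**Across the range (ka 0.8-2):**

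| True t1/2 (h) | t1/2 by 13.6.3 (h) | AUC(0-t) / true 24 h | AUC(0-t) / true 12 h | AUC(0-∞) / true 12 h | t1/2 from samples to 12 h (h) |
|---|---|---|---|---|---|
| 3 | 6.2-8.2 | 0.62-0.65 | 1.24-1.29 | 1.4-1.6 | 3.0-3.1 |
| 6 | 13.4-16.3 | 0.75-0.77 | 1.50-1.55 | 2.3-2.6 | 6.0-6.3 |
| 12 | 26.8-32.7 | 0.86-0.87 | 1.72-1.75 | 4.0-4.7 | 12.0-12.6 |
| 18 | 40.3-49.1 | 0.90-0.91 | 1.80-1.83 | 5.7-6.7 | 18.0-18.9 |
| 36 | 80.6-98.4 | 0.95-0.96 | 1.90-1.91 | 10.6-12.7 | 36.0-37.9 |

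The t1/2 ratio is 2.1-2.7 and the best adjusted R² only 0.55-0.74. Trapezoidal AUC(0-12) is within 4% of the true interval AUC throughout. Part of the AUC(0-∞) excess would exist anyway, because a tail is added to a steady-state profile.

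**Timing.** For a true 6 h (ka 0.8), with the evening dose at 12-14 h and the last sample at 23-25 h, t1/2 reads 15.2-23.4 h.

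**Biexponential kinetics (three assumed profiles).** For true terminal half-lives of 18, 24 and 60 h, the rule gives 20.2, 12.6 and 40.4 h. Using samples to 12 h gives 9.9, 5.5 and 15.1 h. AUC(0-t) is 76-89% of true 24 h exposure.

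**CLB taken twice daily, Day 33/Day 1 ratio of AUC(0-t), clearance halved (true ratio 2.00):**

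| CLB t1/2 on Day 1, assumed (h) | Ratio obtained |
|---|---|
| 6 | 2.26-2.29 |
| 10 | 2.16-2.18 |
| 18 | 2.09-2.11 |
| 36 | 2.05 |

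With no change in clearance the ratio is exactly 1.00. A true 0.5 reads below 0.5.

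**The case against.** **The trial's conclusion does not use these values.** The only decision rule (13.6.3: 90% CI within 0.5 to 2.0) concerns Cmax, AUC(0-t) and AUC(0-∞) of CLB and N-CLB. CBD is measured at Visit 4 only and described. This stands, and it limits the consequence. It does not excuse the rule: a descriptive primary endpoint must still describe the quantity it names.

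**A reader might infer that the CLB no-effect conclusion is compromised.** The documents do not support that. The error needs an evening CLB dose, and the number of such patients is not given. AED regimens must stay stable through the blinded phase (6.1.6), so the same distortion occurs at both visits and mostly cancels. In the model, what remains pushes the ratio away from 1, so it does not favour a false finding of no meaningful effect. These ratios are for AUC(0-t); the evening dose's share of the AUC(0-∞) error was not separated.

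**A reader might also infer that every half-life will be two to three times too long, and that a 12 h cut restores the truth.** Both depend on one-compartment kinetics. In the biexponential cases one estimate is 12% high and two are too low, and the 12 h cut lies further from the true terminal value in all three.

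**The SAP could deal with it.** An SAP is to follow before database lock, and the planned samples already allow AUC(0-12). But 13.6.3 is not silent: it fixes the slope and AUC rules, so a correct SAP would have to depart from the protocol. Its reference to the corresponding administration time does not help, because 9.1.10 times every sample from the morning dose. Re-timed to the evening dose, the 24 h sample would be a 12 h trough of another interval.

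**VPA, STP, LEV and TPM.** They are neither primary nor secondary endpoints and their dosing frequency is not stated, so they add little weight.

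**Conclusion.** The protocol is wrong as written for CBD, its major metabolites and THC. Dosing, sampling and calculation rules together make the 24 h value a second trough. The stated t1/2 is then not an elimination half-life, AUC(0-t) is neither 12 h nor 24 h exposure, and AUC(0-∞) inherits both faults. This follows from the text alone, provided the 24 h value is quantifiable; a steady-state trough should be about as quantifiable as the 12 h one.

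The size rests on assumed kinetics. In one compartment, t1/2 is 2.1-2.7 times too long, and AUC(0-t) is 62-77% of true 24 h exposure at half-lives of 3-6 h, rising to about 95% at 36 h. Outside that model the t1/2 error has no fixed direction. Cmax and tmax are largely unaffected.

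For CLB and N-CLB the effect is conditional on evening dosing and modest: a true AUC(0-t) ratio of 2.0 reads about 2.05-2.3 for half-lives of 36 down to 6 h, and a true 1 is unbiased. It matters mainly near the 0.5 and 2.0 limits.

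**What to change.** In 13.6.3, for any analyte whose parent drug is taken again at about 12 h:
- Report AUC(0-12) as the dosing-interval exposure, in place of AUC(0-t) and AUC(0-∞).
- Use no sample drawn after the evening dose in the terminal fit.
- Report t1/2 as not estimable, or as an apparent 12 h value, where 12 h of data do not support it.
- List the 24 h value as a second trough.

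For CLB and N-CLB, compute the Day 33/Day 1 ratio over each patient's own dosing interval, using the dose times the diary already collects. Reconcile 9.1.10 with the diary instruction in 4.1 on how often CLB is taken.

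The cost is wording and a dosing-interval flag per patient and analyte, with no extra samples or patients and no change to dosing. The real loss is that t1/2 will be unavailable for slow analytes or late peaks: after 4 h only the 6 h and 12 h samples precede the evening dose, so a peak at 4 h or later leaves fewer than three points to fit.
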